10.5. 12-Lead Electrocardiogram	40

10.6. ECOG Performance Status	41
11. Pharmacokinetic Analyses	41
12. Pharmacodynamics and Pharmacogenomic Analyses	42
13. Change from Analyses Planned in Protocol	42
14. References	42

List of Tables

Table 1: Exicorilant Upward Dose Titration for Dose-Determination Segment 2	13
Table 2: Analysis Visit Windows for Safety Assessment	26
Table 3: Censoring Rules for the Primary Analysis of PFS	34

List of Figures

Figure 1: CORT125281-601 Phase 1/2a Schematic	11
---	----

List of Abbreviations

Abbreviation	Definition
λ_z	terminal elimination rate constant
Abi	abiraterone
AE	adverse event
ACTH	adrenocorticotrophic hormone
ALP	alkaline phosphatase
ALT	alanine aminotransferase
ANC	absolute neutrophil count
AR	androgen receptor
ARant	androgen-receptor antagonist
ARV7	androgen-receptor splice variant 7 messenger RNA
AUC	area under the curve
AUC0-24	area under the curve from 0 to 24 hours
AUC0-6	area under the curve from 0 to 6 hours
AUC0-inf	area under the curve from 0 to infinity
AUC0-last	area under the curve from 0 to time of last measurable concentration
BID	twice daily
CI	confidence interval
C _{max}	maximum observed plasma concentration
C _{min}	minimum concentration
CRPC	castration-resistant prostate cancer
CR	complete response
CTC	circulating tumor cell
CYP	cytochrome P450
DLT	dose-limiting toxicity
DNA	deoxyribonucleic acid
DOR	duration of response
DRC	Data Review Committee
ECG	electrocardiogram
ECOG	Eastern Cooperative Oncology Group
eCRF	electronic case report form
EOT	End-of-Treatment
EU	European Union
FACT-P	Functional Assessment of Cancer Therapy-Prostate
GC	glucocorticoid
GCP	Good Clinical Practice
GR	glucocorticoid receptor
HIV	human immunodeficiency virus
HR	hazard ratio
ICH	International Council for Harmonisation

ICF	informed consent form
IHC	immunohistochemistry
LDH	lactic dehydrogenase
mCRPC	metastatic castration-resistant prostate cancer
MedDRA	Medical Dictionary for Regulatory Activities
mRNA	messenger ribonucleic acid
MTD	maximum tolerated dose
NCI-CTCAE	National Cancer Institute Common Terminology Criteria for Adverse
ORR	objective response rate
PCWG3	Prostate Cancer Clinical Trials Working Group 3
PD	pharmacodynamic(s)
PK	pharmacokinetic(s)
PR	partial response
PRO	patient-reported outcome
PSA	prostate-specific antigen
QD	once daily
QoL	quality of life
RP2D	recommended Phase 2 dose
RECIST	Response Evaluation Criteria in Solid Tumors
RNA	ribonucleic acid
rPFS	radiographic progression-free survival
SAE	serious adverse event
SoA	Schedule of Assessments
SOC	system organ class
SOP	Standard Operating Procedure
SSE	symptomatic skeletal event
TEAE	treatment-emergent adverse event
T _{max}	time to reach C _{max}
T _{last}	time after dosing of the last quantifiable concentration
UFC	urinary free cortisol
ULN	upper limit of normal
US	United States
WHO	World Health Organization
WHODD	WHO Drug Dictionary

1. Introduction

1.1. Background

Prostate cancer growth, driven by androgens, routinely involves androgen deprivation therapy with gonadotropin-releasing hormone analogues for patients with locally advanced or metastatic prostate cancer. Approved hormone-based therapies such as abiraterone, which inhibits androgen synthesis, and enzalutamide, an androgen receptor (AR) antagonist, have demonstrated a survival advantage in both post-docetaxel as well as chemotherapy-naïve patients. In patients with castration-resistant prostate cancer (CRPC) treated with anti-androgen therapy, the glucocorticoid receptor (GR) can become the dominant growth factor and provides a mechanism of resistance to drugs such as enzalutamide. The present study hypothesizes that treatment with a GR antagonist in combination with enzalutamide will overcome a mechanism of resistance to androgen-targeted therapies, and thereby provide clinical benefit to patients with metastatic CRPC (mCRPC), compared with enzalutamide alone, as well as to patients who have developed enzalutamide resistance.

CORT125281 (International nonproprietary name: exicorilant, which will be used throughout the statistical analysis plan (SAP) instead of CORT125281), a selective GR modulator, is being developed for treatment of mCRPC.

CORT125281-601 is a Phase 1/2a, dose-determination and expansion study conducted in patients with mCRPC to evaluate the safety, tolerability, pharmacokinetics (PK), pharmacodynamics (PD), and preliminary efficacy of exicorilant in combination with enzalutamide. The primary objective of this study is to determine the maximum tolerated dose (MTD) and/or biologically active doses of exicorilant in combination with enzalutamide and to identify the recommended Phase 2 dose (RP2D).

Details of the analyses required to address study objectives are presented in this Statistical Analysis Plan (SAP). This SAP has been developed and will be approved prior to data unblinding and data analysis. All analyses supporting the clinical study report (CSR) will be conducted after clinical trial data are entered into the database, discrepancies resolved, and the database is authorized (closed to further changes). Any deviations from the SAP will be documented as such in the study report. Additional exploratory biomarker analyses of these and other assessments may be conducted and described in a separate Biomarker SAP.

Production and quality control of statistical analyses and accompanying tables, listings, and figures (TLFs) will be the responsibility of [REDACTED] with appropriate oversight by Corcept Therapeutics Biometrics team.

1.2. Protocol and Amendment History

This SAP is based on Amendment 5 of Protocol CORT125821-601, which incorporates the following Amendments:

Version	Approval Date	Major Changes, if any*
Protocol	16 August 2017	
Amendment 1	29 September 2017	Modified the definition of DLTs
Amendment 2	19 December 2017	Updated entry criteria, clarified the definition of MTD and clarified performing AE assessments and SAE reporting
Amendment 3	09 January 2018	Added additional data from Phase 1 study, clarified dosing schema, added requirement for sentinel dosing, revised the Section of Statistical Methods
Amendment 4	25 July 2018	Modified entry criteria and clarified QOL collections
Amendment 5	21 February 2020	Study design updated to include segment 2 of randomized double-blind portion, under once daily fed conditions
* Changes expected to require accommodation in analysis plan.		

2. Study Design

2.1. Design Overview

[figure not shown]
This is a Phase 1/2a dose-determination and expansion study conducted in patients with mCRPC to evaluate the safety, tolerability, PK, PD, and preliminary efficacy of exicorilant in combination with enzalutamide; and to identify the RP2D. This open-label study consists of 2 phases: a Dose-Determination Phase (Phase 1) and an Expansion Phase (Phase 2a). The Dose-Determination Phase is made up of 2 segments: Segment 1 (an open-label, twice daily exicorilant) and Segment 2-double-blind, once daily exicorilant under fed conditions). [Figure 1](#) shows the overall schematic for the study design.

Patients will participate in the following study periods:

- Screening Period will take place within 28 days before the first dose of study treatment
- Lead-In Period:

- Dose-Determination Phase Segment 1: Enzalutamide monotherapy for 28 days was planned. This may be updated per Data Review Committee (DRC) data review.
- Dose-Determination Phase Segment 2: No Lead-In Period is planned.
- Expansion Phase:
 - Food-Effect Subcohort: A single dose of exicorilant under fasting conditions on Cycle 1 Day -7, and a single dose of exicorilant 30 minutes after a standard breakfast on Cycle 1 Day 1
 - Non-Food-Effect Patients: No Lead-In Period
- Combination Treatment Period: Patients will take combination treatment (exicorilant and enzalutamide) until reaching disease progression, experiencing unmanageable toxicity, or until other treatment discontinuation criteria are met. Patients will continue assessments per the Schedule of Assessments (SoA) for the Combination Treatment Period until both exicorilant and enzalutamide are discontinued.
- Follow-Up Period: Patients will return for a Post-Treatment Follow-Up Visit (End-of-Treatment +30 Days Visit) 30 days after their final dose of exicorilant or enzalutamide, whichever is later. After this, patients will continue to be followed for progression, information on subsequent anticancer therapies (start and end date and response) and survival.

Figure 1: CORT125281-601 Phase 1/2a Schematic

2.2. Phase 1, Dose-Determination Segment 1 (Open-Label)

Segment 1 of the Dose-Determination Phase is designed to determine dose limiting toxicity (DLTs), the MTD/biologically active doses and the RP2D of exicorilant + enzalutamide in patients with mCRPC. Each cohort must include a minimum of 3 evaluable patients, but can enroll up to 9 patients for dose optimization and selection of the RP2D. The DRC may make the recommendation to adjust the size of a cohort to more than 9 patients to further evaluate a given dose (eg, based on PK data or tolerability). A minimum of 3 evaluable patients in each cohort must complete 28 days of continuous combination treatment with enzalutamide and exicorilant and have safety data reviewed by the DRC prior to proceeding to the next dose level. If <33% of the DLT-evaluable patients have experienced a DLT (see Protocol Section 5.5 for definition), then enrollment may proceed in the next cohort. If $\geq 33\%$ of the DLT-evaluable patients have experienced a DLT in a cohort, then recruitment to that cohort will be discontinued, and this dose will be determined to be not tolerated. Dose escalation of exicorilant will initially be in up to doubling steps until any DLT or Grade 2 toxicity attributed to exicorilant is reported; thereafter, dose escalation will be in $\leq 50\%$ steps. The starting dose for the subsequent cohort will be per the DRC recommendation and will be based upon tolerability and observed toxicity in previous cohorts (including DLTs), human PK, PD markers of target engagement, projected efficacious exposures, and the available capsule strengths. The DRC may adjust the dose of enzalutamide in subsequent cohorts based on PK and tolerability.

2.3. Phase 1, Dose-Determination Segment 2 (Double-Blind)

Segment 2 of the Dose-Determination Phase is randomized and double blinded for dose titration with respect to exicorilant in combination with enzalutamide. All patients will receive exicorilant at a starting dose of 240 mg once daily (QD) under fed conditions. Approximately 20 patients will be enrolled to achieve 16 DLT-evaluable patients randomized in a 3:1 ratio to receive exicorilant in combination with enzalutamide either with the starting dose of exicorilant 240 mg QD with dose titration to 320 mg QD (N=12; Arm A) or with the starting dose of exicorilant 240 mg QD, without an increase of the active dose (N=4; Arm B). Patients in Arm B will receive placebo capsules, such that the patient, Investigators, and study team are blinded to which dose patients are receiving (ie, 240 mg QD versus 240 mg to 320 mg QD). In Segment 2, all doses of exicorilant should be taken with food.

All patients will start treatment with exicorilant 240 mg QD on Cycle 1 Day 1. Patients will continue on their current dose of enzalutamide during the Screening Period and at the initiation of exicorilant. Beginning on Cycle 1 Day 16, the dose of exicorilant will be increased in 40-mg increments every 2 weeks, as tolerated, with either exicorilant (Arm A; N=12) to a maximum dose of exicorilant 320 mg QD or with placebo (Arm B; N=4) (Table 1). If any planned dose escalation is postponed due to transient intolerable Grade 2 toxicity or scheduling conflicts (delays in escalation

not due to toxicity), the dose may be escalated within 14 days of the planned escalation.

- **Arm A (N=12):** exicorilant 240 mg QD under fed conditions with upward dose titration in combination with enzalutamide. Exicorilant will be increased in 40-mg increments every 2 weeks (+14-day window) based upon tolerability to a maximum dose of 320 mg QD (Table 1).
 - Cycle 1 Day 1: exicorilant 240 mg QD
 - Cycle 1 Day 16 (+14-day window): exicorilant 280 mg QD
 - Cycle 2 Day 2 to Cycle 2 Day 16 (+14-day window): exicorilant 320 mg QD
- **Arm B (N=4):** exicorilant 240 mg QD under fed conditions, with an increase in the number of placebo capsules every 2 weeks (+14-day window) (Table 1).
 - Cycle 1 Day 1: exicorilant 240 mg QD
 - Cycle 1 Day 16 (+14-day window): exicorilant 240 mg QD
 - Cycle 2 Day 2 to Cycle 2 Day 16 (+14-day window): exicorilant 240 mg QD

Table 1: Exicorilant Upward Dose Titration for Dose-Determination Segment 2

Dose Level	Resulting exicorilant Dosage (QD)		Open-Label Bottle (exicorilant)	Blind-Label Bottle (exicorilant or Placebo) ^a
	Arm A	Arm B		
1 (Starting Dose)	240 mg	240 mg	6 capsules	0 capsules
+1 (First Increase)	280 mg	240 mg	6 capsules	1 capsule
+2 (Second Increase)	320 mg	240 mg	6 capsules	2 capsules

QD, once daily.

Note: The exicorilant dosage will be escalated in 2-week intervals unless there are intolerable Grade 2 toxicities, dose-limiting toxicities, or Grade 3 or greater toxicities attributed to exicorilant (Protocol Section 5.7).

^a Note: The blind-label bottle contains blinded capsules (exicorilant [Arm A] or placebo [Arm B]). During the double-blind portion of the Dose-Determination Phase (ie, Segment 2), an unblinded Medical Monitor independent of the study team will provide additional oversight for the study, including review of serious unexpected adverse events (AEs) considered related to either exicorilant or enzalutamide and DLTs.

After all patients complete 3 cycles of treatment or discontinue treatment, the data will be unblinded and the DRC will meet to review the safety and available PK and PD data. The DRC will evaluate the frequency of DLTs, the DLT rate (the number of DLTs per week [7-day period] during the DLT-evaluation period), and overall tolerability in their assessment of the dose titration regimen as the Phase 2 RP2D. If the DLT rate for the regimen is $\geq 33\%$, alternative titration schemes may be considered as the regimen for the RP2D, such as greater time increments between dose escalations or limiting the upper range of the regimen to those dose levels corresponding to a DLT rate of $< 33\%$. Once the DRC has determined the RP2D,

patients assigned to Arm B who have not experienced dose reductions due to toxicity will have their exicorilant dose escalated per the recommended Phase 2 regimen.

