5.12 Blinding

5.12.1 Dose-Determination Phase Segment 1 and Expansion Phase

The Phase 1 Segment 1 and Phase 2a parts of the study are open label. No blinded study treatments will be used in these parts of the study.

5.12.2 Dose-Determination Phase Segment 2

The Phase 1 Segment 2 part of the study is double blinded for dose titration with respect to CORT125281 in combination with enzalutamide. All patients will receive CORT125281 at a minimum starting dose of 240 mg QD. Approximately 20 patients will be enrolled to achieve 16 DLT-evaluable patients randomized. Randomization will be conducted by IRT in a 3:1 ratio to receive CORT125281 in combination with enzalutamide either with the starting dose of CORT125281 240 mg with dose- titration to 320 mg QD (N=12; Arm A) or with the starting

dose of CORT125281 240 mg, without titration of the dose (N=4; Arm B). Dose titration of CORT125281 in Arm B will occur with placebo, such that the patient, Investigators, and study teams are blinded to which patients are receiving (ie, 240 mg versus 240 mg to 320 mg). During this part of the study, an unblinded Medical Monitor independent of the study team will provide additional oversight for the study, including review of serious unexpected AEs considered related to either CORT125281 or enzalutamide and DLTs. After all patients complete 3 cycles of treatment or discontinue treatment, the data will be unblinded and the DRC will meet to review the safety and available PK and PD data (Section 9.8). Once the DRC has determined the RD, patients assigned to Arm B who have not experienced any dose reductions due to toxicity will then have their dose escalated in an open-label fashion per the recommended upward titration regimen.

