9.1 General Statistical Considerations

The key primary and secondary objectives of the study are to determine the MTD and/or biologically active doses of CORT125281 in combination with enzalutamide, and to evaluate safety and tolerability and to characterize preliminary efficacy of CORT125281 in combination with enzalutamide. All study data will be summarized using descriptive statistics. Means, standard deviations, medians, maximum and minimum values will be used to summarize continuous variables. Frequencies and proportions will be used to summarize categorical variables. Time-to-event endpoints will be summarized using Kaplan-Meier method.

In Dose-Determination Phase Segment 1 and in the Expansion Phase, all summaries will be presented by treatment regimen dose group and overall. In the Dose-Determination Phase Segment 2, all analyses will be presented by treatment arm and overall.

Baseline will be defined as the last measurement collected before the first dose of study treatment (CORT125281 or on-study enzalutamide, whichever is earlier).

All analyses will be completed using version 9.3 or later of the SAS Statistical Analysis System (SAS Institute, Inc, Cary, NC).

Detailed procedures for statistical analyses to be performed for this study will be provided in a separate Statistical Analysis Plan that will be finalized before database lock.

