8.7. Treatment Exposure and Compliance

All recorded information on oral dosing of exicorilant and enzalutamide, including dose level, frequency, and reason for dose interval changes will be presented in a data listing by date of administration. Note that daily dose was printed on the CRF, yet the data collected were dose level. To calculate the daily dose, we multiply the dose level with frequency. For the frequency of BID, the multiplier is 2. That is, daily dose equals to the dose level times 2. For the frequency of QD, the multiplier is 1. That is the dose level is the same as the daily dose.

A table by treatment regimen dose group/arm and overall will provide summary statistics on the following:

1) Number of Cycles of Treatment:

The number of cycles for each study drug will be presented based on the last visit when the patient received treatment with non-zero and non-missing dose. The number of cycles for each study drug will be calculated as duration of exposure in weeks/4.

2) Duration of Exposure:

The duration of exposure for each study drug will be presented in weeks and calculated as (the date of last non-zero and non-missing dose of study drug before drug discontinuation - the date of the first dose of study drug + 1)/7. Please note that if a patient had a lead-in period of a study medication, then the date of first dose for that study medication is the date of first dose in the lead-in period. If no lead in period, then start date of study drug is Cycle 1 Day 1.

3) Total Dose Received:

The total dose received for each study drug will be the sum of the actual dose administered during the duration of exposure. For subjects where their dose received is either zero or missing prior to drug discontinuation, a received dose of zero is included in the total dose received derivation.

4) Total dose expected:

The total dose expected is calculated for each study drug. The expected drug dosing schedule and the protocol-specified dose escalations, if any, is used in combination with the actual date and dose of study drug administration to calculate the total dose expected.

For Segment 1 of the Dose Determination Phase, the starting dose for both drugs in each cohort is its expected dose level.

For Segment 2 of the Dose Determination Phase, a protocol-specified dose escalation is expected for patients randomized to the Arm A group.

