- The expected dose of exicorilant for Segment 2 Arm A patient is 240 mg QD from Cycle 1 Day 1 to Cycle 1 Day 14, 280 mg QD from Cycle 1 Day 15 to Cycle 1 Day 28, and 320 mg QD thereafter.
- The expected dose of exicorilant for Segment 2 Arm B patient is 240 mg QD.
- The expected dose of enzalutamide for Segment 2 patient is patient's currently tolerated dose through the Screening Period and the initiation of exicorilant.

5) Relative dose intensity:

Relative dose intensity is calculated for each study drug as the total dose received divided by the total dose expected, multiplied by 100.

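### Arm B patients may be escalated open-label after the Segment 2 review, but SAP 8.7 keeps their expected dose at 240 mg QD and the final safety tables do not separate the later period

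*SAP*

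**What the plan says.** **The escalation is planned.** SAP 2.3 gives the order: "After all patients complete 3 cycles of treatment or discontinue treatment, the data will be unblinded and the DRC will meet". Once the Data Review Committee (DRC) has set the regimen, Arm B patients without a toxicity-related reduction "will have their exicorilant dose escalated per the recommended Phase 2 regimen". Protocol 5.12.2 adds that they "will then have their dose escalated in an open-label fashion per the recommended upward titration regimen". Protocol 5.4.2 and 5.8.1.2 describe the same step.

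**The expected dose does not follow it.** SAP 8.7 states that "a protocol-specified dose escalation is expected for patients randomized to the Arm A group" and then that "The expected dose of exicorilant for Segment 2 Arm B patient is 240 mg QD". The Arm B line has no end date and no later step. On the other side of the ratio, "The total dose received for each study drug will be the sum of the actual dose administered during the duration of exposure", and "Relative dose intensity is calculated for each study drug as the total dose received divided by the total dose expected, multiplied by 100". Neither rule stops at unblinding.

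**Reporting is by arm, without a cut.** Protocol 9.1 says that for Segment 2 "all analyses will be presented by treatment arm and overall". SAP 7.2 and 10.1 run the treatment-emergent period from the first exicorilant dose until 30 days past the final dose. SAP 1.1 places the study-report analyses after database closure, so post-escalation data are included.

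**The concern.** Arm B is the only randomised group held at a fixed 240 mg. Patients who escalate leave that dose by plan, yet neither document ends, splits or relabels their data at that point. Two things follow in the final report if the recommended regimen exceeds 240 mg.

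- Adverse events, laboratory values, vital signs and ECGs recorded at 280 or 320 mg are summarised under the 240 mg arm. They come from patients selected for having had no toxicity-related reduction.
- Relative dose intensity divides what the patient took by a dose he was no longer assigned. A patient who followed the protocol exactly then appears over-dosed, and one who missed doses appears more adherent than he was.

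With 4 planned Arm B patients, or about 5 if 20 are enrolled at 3:1, one escalated patient is enough to change the column.

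**Working it through.** The plan states no relative dose intensity (RDI) figure, so there is none to reproduce. Two related figures agree with the documents: 6, 7 and 8 capsules × 40 mg = 240, 280 and 320 mg (SAP Table 1), and 75% of 84 days = 63 days (SAP 8.8).

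**Inputs from the documents.** Arm B expected dose is 240 mg QD and RDI is received/expected × 100 (SAP 8.7). The top of the titration under test is 320 mg QD (SAP 2.3). Escalation comes after every Segment 2 patient has completed 3 cycles (84 days) or stopped, so day 85 is the earliest possible start.

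**Assumptions, not in the documents.** The first escalated dose falls on day 85, 141, 169 or 253. The patient takes 280 mg for 14 days, then 320 mg. Adherence is full unless stated otherwise.

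**Formula.** RDI = 100 × (240·d₁ + 280·d₂ + 320·d₃) / (240·T), where d₁, d₂ and d₃ are the days at each dose and T is their sum. At T = 336 the denominator is 240 × 336 = 80,640 mg.

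| First escalated dose | Days at 240 / 280 / 320 mg | Received (mg) | RDI | Days above 240 mg |
|---|---|---|---|---|
| Day 85 | 84 / 14 / 238 | 100,240 | 124.3% | 75.0% |
| Day 141 | 140 / 14 / 182 | 95,760 | 118.8% | 58.3% |
| Day 169 | 168 / 14 / 154 | 93,520 | 116.0% | 50.0% |
| Day 253 | 252 / 14 / 70 | 86,800 | 107.6% | 25.0% |

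The last column is the share of treatment days that still counts as 240 mg exposure in the safety tables.

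**Shorter follow-up.** For a day-85 start, RDI is 115.3% at day 168 and 121.3% at day 252.

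**Limits.** 320/240 = 133.3%. If the regimen stops at 280 mg, the limit is 280/240 = 116.7%. The day-336 values are then (84 × 240 + 252 × 280)/80,640 = 112.5% for a day-85 start and (252 × 240 + 84 × 280)/80,640 = 104.2% for a day-253 start.

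**Adherence.** With adherence a and a share p of days at 320 mg (ignoring the 280 mg step), RDI = 100 × a × (1 + p/3). It passes 100% only if p > 3(1/a − 1). The threshold is 16% of days at a = 0.95 and 33% at a = 0.90; at a = 0.75 or below it cannot be met. The inflation remains below 100%: at 90% adherence and a day-253 start, RDI is 0.90 × 107.6% = 96.9% instead of 90%.

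**After the fix.** If the expected dose follows the assigned regimen, or exposure is cut at escalation, full adherence gives 100% and 90% adherence gives 90%.

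**Event rates.** One event moves the Arm B rate by 1/4 = 25 points, or 1/5 = 20 points. That holds for any event in so small an arm. What matters here is which dose the event is credited to.

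**The case against.** The strongest case on the other side has five parts.

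1. **The dose decision is made before any escalation.** This stands in full. A reader might infer that the dose-toxicity comparison behind the recommended dose is contaminated. The documents do not support that. The DLT window and the patient-week denominator end at 12 weeks (SAP 4.1, 8.8), and the DRC's whole review of safety, PK, PD and tolerability precedes Arm B escalation (SAP 2.3; Protocol 9.9).
2. **SAP 8.7 can be read more kindly.** Its general sentence on total expected dose allows for escalations that the protocol specifies, and the Arm B step is one. But the lines that apply this sentence name only Arm A and give Arm B a flat 240 mg. At best the section is ambiguous.
3. **Some summaries also use a dose group.** SAP 8.7, 10.3, 10.4, 10.6 and 12 refer to a treatment regimen dose group as well as, or in place of, arm. The term is never defined, so a dose-based display is neither promised nor excluded. SAP 8.8 tabulates by highest dose received, but only for DLTs. Dated listings let a reader trace single events; they do not correct the tables.
4. **Arm A also mixes doses.** True, but its mixture is the assigned regimen and its expected dose follows it. Arm B after escalation meets neither condition.
5. **Cutting efficacy at escalation would do harm.** This stands. Censoring rPFS, survival or skeletal events at a switch that depends on tolerating treatment may be informative.

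The analyses are also descriptive (Protocol 9.3), which limits the consequence to misreading the final tables.

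**Conclusion.** The point holds for the final exposure and safety summaries, and only there. The stated rules give escalated Arm B patients the wrong expected dose and place their higher-dose events in the 240 mg column.

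It arises only if the recommended regimen exceeds 240 mg and an Arm B patient with no toxicity-related reduction is still on treatment when it is set. Under the assumed 14-day step to 320 mg, a fully adherent patient shows 107.6% to 124.3% at day 336 instead of 100%, with limits of 133.3% (320 mg) and 116.7% (280 mg).

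Two further readings go too far. RDI above 100% is not a property of every Arm B patient, since it also depends on adherence. Figures of 117%, 122% and 125% at days 168, 252 and 336 need a direct move from 240 to 320 mg on day 85; the documents describe an upward titration, and day 85 is the earliest date. It should be corrected before database lock, but it does not threaten the Segment 2 dose decision.

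**What to change.** - **SAP 8.7, expected dose.** State that the Arm B expected dose is 240 mg QD up to the first open-label escalated dose and follows the patient's assigned regimen from then on.
- **SAP 8.7 and 10, exposure and safety.** Summarise Arm B up to the day before that dose. Show later data in a separate column for Arm B after escalation, with adverse events assigned by onset date.
- **SAP 9, time-to-event endpoints.** Keep rPFS, overall survival, time to skeletal event and the others by randomised arm with full follow-up, and footnote the escalation. Any version cut at escalation should be a sensitivity analysis only.

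No dosing rule or data collection changes. The cost is SAP wording, one extra column and a little programming.
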